## **ABSTRACT**

**Background:** Although proton pump inhibitor (PPI) can prevent recurrent peptic ulcer in clopidogrel users with a history of peptic ulcer, the interaction between PPIs and clopidogrel has drawn much attention recently. Several studies reported that certain PPIs could reduce clopidogrel's antiplatelet effects and increase cardiovascular events. These data suggested that PPIs may potentially inhibit the CYP2C19 pathway and interfere with the conversion of clopidogrel to active form. Therefore, searching for other gastroprotective agents such as histamine-2 receptor antagonist (H2RA) to prevent gastrointestinal events for clopidogrel users is urgently needed in clinical practice.

**Aims:** To compare the efficacy of PPI and H2RA for the prevention of recurrent peptic ulcers in thienopyridine users.

**Methods:** We plan to enroll 334 thienopyridine (clopidogrel or ticlopidine) users without baseline gastroduodenal ulcer at initial endoscopy. The patients will be randomly assigned to receive either (1) pantoprazole (40 mg qd) or (2) famotidine (40 mg qd) for 6 months. Blood sampling for genotyping of *CYP2C19* is carried out on enrollment. Follow-up endoscopy is carried out at the

end of the 6th month and whenever severe epigastric pain, hematemesis or melena occurs. The primary end point is the occurrence of gastric and/or duodenal ulcers during the 6-month study period.

## INTRODUCTION

Platelet activation and aggregation play an important role in the pathogenesis of arterial thrombosis and lead to ischemic events. Thienopyridine (clopidogrel or ticlopidine) inhibits platelet function by selectively and irreversibly blocking the adenosine diphosphate (ADP) receptor on platelets, thereby affecting ADP-dependent activation of the GpIIb-IIIa complex, the major receptors for fibrinogen present on the platelet surface. Alone or in association with aspirin, clopidogrel is a thienopyridine, which has successfully proved to be beneficial in the treatment of acute coronary syndrome and prevention of ischemic events in patients with atherosclerotic diseases.

The CAPRIE study showed that long-term administration of clopidogrel to patients with atherosclerotic vascular disease is more effective than aspirin in reducing the combined risk of ischemic events. Additionally, Clopidogrel induced fewer episodes of gastrointestinal bleeding than aspirin. The American College of Cardiology-American Heart Association guidelines therefore recommend clopidogrel as an alternative to aspirin for patients with unstable angina or non-ST-segment elevation myocardial infarction who have an aspirin intolerance.

However, a recent study from our center demonstrated that 11% of the patients with a peptic ulcer history who took clopidogrel for the prevention of ischemic events had recurrent peptic ulcer during a 6-month follow-up period. Another prospective study also showed 9% of patients with a history of peptic ulcer bleeding who took clopidogrel had recurrent ulcer bleeding within

one year. The mechanisms leading to recurrent peptic ulcers and ulcer bleeding among patients receiving clopidogrel are unclear. Nonetheless, an animal study revealed that platelet ADP-receptor antagonists impair the healing of gastric ulcers by suppressing the release of platelet-derived growth factors. Platelet aggregation plays an important role in ulcer healing through the release of platelet-derived growth factors that promote angiogenesis, which is important for ulcer healing. An endoscopic study revealed that a point prevalence of peptic ulcer was 1.3% in the adult general population. Although clopidogrel might not be primarily responsible for the development of peptic ulcer, it may impair healing of background ulcers and convert silent ulcers to bleeding lesions.

Our previous study has proved that esomeprazole can effectively prevent recurrent peptic ulcers among clopidogrel users with a history of peptic ulcer. Currently, very few studies have evaluated the efficacy of histamine-2 receptor antagonist (H2RA) in the prevention of GI injury with antiplatelet agents. Ng et al. showed that H2RA is inferior to proton pump inhibitor (PPI) in preventing recurrence of aspirin-related peptic ulcers or erosions in patients with aspirin-related peptic ulcers/erosions. A recent case-control study by Lanas et al. revealed that, compared with patients undergoing antiplatelet therapy without protective co-therapy, H2RAs can significantly reduce the risk of upper GI bleeding in patients taking low-dose aspirin but not in those taking clopidogrel. Another cohort study also reported that 22% of clopidogrel users taking concomitant H2RAs had recurrent upper GI bleeding after a 1-year follow up, whereas no patient taking clopidogrel plus a PPI had recurrent bleeding.

Recently, the interaction of PPIs and thienopyridines has raised the concern for the safety of combination use of the two medicines. Thienopyridines are prodrugs, which must be absorbed in the gastrointestinal tract, and metabolized in the liver to generate active metabolites and acquire their anti-platelet properties. The metabolism of thienopyridines involve CYP2C19 isoenzyme, which is also the key enzyme for the metabolism of most PPIs. This has led to the assumption that some PPIs may potentially inhibit the CYP2C19 pathway and interfere with the conversion of thienopyridines to active form. Three large retrospective observation studies also reported that patients prescribed clopidogrel who also took PPIs had significant increases in cardiovascular events. However, Bhatt et al. recently conducted a double-blind, prospective randomized trial (COGENT; Clopidogrel and the Optimization of Gastrointestinal Events Trial) to investigate the effect of omeprazole in patients receiving both aspirin and clopidogrel. The data demonstrated that prophylactic use of omeprazole reduces the rate of upper GI bleeding among patients receiving aspirin and clopidogrel, and there were no differences in CV events between omeprazole and placebo groups.

Our recent study demonstrated that esomeprazole does not influence the action of clopidogrel on platelet aggregation when doses of esomeprazole and clopidogrel are widely separated. However, whether H2RA may interfere with the conversion of thienopyridines to active form remain unclear. Therefore, we design the randomized double-blind comparison study to investigate whether proton pump inhibitor is superior to H2RA in the prevention of recurrent peptic ulcers in thienopyridine users.

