## **Study Protocol**

### ***Randomization and treatment***

Eligible patients are randomly assigned to receive either (1) 40 mg of famotidine daily or (2) 40 mg of pantoprazole daily for 6 months. Randomization is carried out with the use of a computer-generated list of random numbers. An independent staff member assigns the treatments according to consecutive numbers that are kept in sealed envelopes. Anticoagulants, cyclooxygenase-2 inhibitors, conventional NSAIDs, aspirin, over-the-counter analgesics, corticosteroids, misoprostol, sucralfate are prohibited. The administration of an antacid (Iwell, Everest, Taiwan) is permitted for the control of dyspeptic symptoms. Compliance with the regimen is assessed by counting the pills that are returned. If *Helicobacter pylori* (*H pylori*) infection is documented on recruitment, a seven-day course of anti-*H pylori* therapy is administered. Urea breath test is performed at four weeks after the end of anti-*H pylori* therapy.

Blood sampling for genotyping of *CYP2C19* is carried out on enrollment. Platelet aggregation tests are performed in Day 1 and Day 28. The *CYP2C19* genotype is determined using the polymerase chain reaction-restriction fragment length polymorphism (PCR-RFLP) as previous description. Genotypes are classified into three groups: homogeneous extensive metabolizer

(homEM; *CYP2C19\*1/CYP2C19\*1*); heterogeneous extensive metabolizer (hetEM; *CYP2C19\*1/CYP2C19\*2* and *CYP2C19\*1/CYP2C19\*3*); poor metabolizer (PM; *CYP2C19\*2/CYP2C19\*2*, *CYP2C19\*2/CYP2C19\*3*, and *CYP2C19\*3/CYP2C19\*3*).

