### ***Follow-up***

Patients are followed up as outpatients with visits every month. Upper gastrointestinal and cardiovascular symptoms are assessed at each visit. They are asked to return to the outpatient clinic if they have persistent dyspeptic symptoms (epigastric pain, fullness, nausea or vomiting) and to report to the emergency room if they have evidences of gastrointestinal bleeding (hematemesis, melena, or sudden onset of severe epigastric pain), cardiovascular events (chest pain, syncope, or sudden onset of severe palpitation) or cerebrovascular accidents (conscious disturbance, hemiparesis, or dysphagia). Follow-up endoscopy with biopsy for urease test is performed whenever persistent dyspepsia, severe epigastric pain, hematemesis or melena occurred and at the end of the 6th month. The endoscopists who performed follow-up endoscopy are unaware of the treatment group assignments. The events of acute coronary syndrome and cerebral vascular accidents during the study period are carefully monitored and assessed.

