### ***End points***

The primary end point is the occurrence of gastric and/or duodenal ulcers, as determined by endoscopy, during the 6-month study period. An ulcer is defined as a circumscribed mucosal break at least 0.5 cm in diameter (measured using endoscopy forceps) and with a perceptible depth. Only events that are confirmed by the adjudication committee and that occurred during treatment are included in the analysis. Patients who do not have follow-up endoscopic examination are assumed to have had normal findings.

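### Does the double-blind label fail because the protocol describes masking only for the follow-up endoscopists?

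*Protocol*

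**What the plan says.** The closing paragraph of the Introduction gives the design label: "we design the randomized double-blind comparison study to investigate whether proton pump inhibitor is superior to H2RA". This is the only place where the protocol applies a blinding term to this trial; the Abstract mentions random assignment alone.

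Under Randomization and treatment, the two regimens are named: "Eligible patients are randomly assigned to receive either (1) 40 mg of famotidine daily or (2) 40 mg of pantoprazole daily for 6 months". The allocation list is computer-generated, and "An independent staff member assigns the treatments according to consecutive numbers that are kept in sealed envelopes". Matched appearance, dummy tablets, coded packs and a code-breaking procedure are not mentioned.

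The Follow-up section has the one explicit masking statement: "The endoscopists who performed follow-up endoscopy are unaware of the treatment group assignments". It also sets the timing of endoscopy, which is "performed whenever persistent dyspepsia, severe epigastric pain, hematemesis or melena occurred and at the end of the 6th month".

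The End points section defines an ulcer by a measured minimum diameter of 0.5 cm plus perceptible depth, and adds two rules: "Only events that are confirmed by the adjudication committee and that occurred during treatment are included in the analysis" and "Patients who do not have follow-up endoscopic examination are assumed to have had normal findings".

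**The concern.** Sealed envelopes conceal the next assignment. They do not control what patients and clinicians know over the following six months. Two different active drugs normally need matched or dummy supply to be indistinguishable, and none is described. Read literally, the methods support an endoscopist-blinded trial, while the Introduction claims more.

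Three steps of the primary end point could respond to knowledge of treatment even when the endoscopist is masked: whether a patient's symptoms lead to an extra endoscopy, whether the committee confirms the event, and whether the patient attends endoscopy at all, since non-attenders are counted as ulcer-free. Expectations are not neutral either: the Introduction cites evidence that an H2RA is inferior to a PPI for aspirin-related ulcers, and the trial sets out to show PPI superiority. At stake would be some differential ascertainment, and a report claiming a stronger design than the one carried out.

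**Working it through.** The question is whether the statements conflict and, if they do not, whether the silence affects the result. The plan gives no figure on masking to reproduce.

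**1. Does any statement contradict the label?**

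| Step | What the protocol states | Compatible with double-blind? |
|---|---|---|
| Assignment | Independent staff member, consecutive numbers, sealed envelopes | Yes; fits numbered coded supply as well as open supply |
| Treatment | Famotidine or pantoprazole, 40 mg daily each | Yes; appearance and packaging not stated |
| Follow-up endoscopy | Endoscopists unaware of assignment | Yes |
| Adjudication | Committee confirms events | Yes; masking not stated |
| Patients and treating clinicians | No separate statement | Yes; nowhere said to know the drug |

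No row conflicts with the Introduction. The gap is one of detail.

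**2. If patients or clinicians did know the drug, what could change?**

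- *Extra endoscopies.* Every patient is also due an endoscopy at the end of month 6. An additional symptom-driven examination matters mainly for an ulcer that would otherwise have healed by then. The protocol gives no rate for this, so no size can be attached.
- *Adjudication.* Ulcers are determined by endoscopy, and the endoscopists are masked. As worded, the committee confirms or rejects what they report. It can remove a reported ulcer but not create one, and the 0.5 cm and depth criteria limit its discretion.
- *Missing endoscopy.* Counting non-attenders as normal is a missing-data rule to be judged on its own merits. It bears on masking only if attendance differs between arms because treatment is known, and nothing in the protocol indicates that.

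**3. How much does one event weigh?**

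Inputs: 334 patients (Abstract); 1:1 allocation (assumed); 11% six-month recurrence in clopidogrel users with an ulcer history, from the earlier study cited in the Introduction (assumed to apply to one arm).

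- Per arm: 334 / 2 = 167.
- One event: 1 / 167 = 0.60 percentage points of an arm's rate.
- Ulcers at 11%: 0.11 × 167 = 18.4, about 18.
- Two-sided p for 18 v 8: 0.041 (uncorrected chi-square), 0.064 (Fisher).
- Two-sided p for 18 v 9: 0.071 (chi-square), 0.107 (Fisher).

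One event can therefore move the chi-square result across 0.05. The splits were chosen to straddle that boundary, and the same holds for any binary end point in a trial of this size, masked or not. The 11% is also a doubtful guide, since both arms here receive acid suppression. These figures describe fragility near a threshold and do not measure bias from incomplete masking.

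**The case for a change.** The strongest case for a change is that who is masked, and how the supply achieves it, is trial conduct. It belongs in the protocol and is not usually left to a statistical analysis plan. The section where it would appear is available and silent. Masking the endoscopist protects the reading of an examination that takes place, not whether it takes place or whether its result is confirmed. The remedy would also be cheap: a few sentences on masking and supply, or a more modest label, plus redaction of allocation from the committee's material.

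Most of this stands as a matter of good documentation. The protocol would be clearer if it named the masked parties and included the adjudication committee among them. It does not follow that the plan is wrong. Each proposed remedy either writes down how the stated design is delivered or applies only if the stated design is not followed, and the document does not suggest the latter. The argument from silence has a further limit: the available text lacks its front page and stops at the End points section, and the methods cite references 27 and 28 although the list shown ends at 23. This does not prove that masking details exist elsewhere, but it cautions against treating their absence here as decisive.

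**Conclusion.** No change to the plan is needed. The observation is accurate: the trial is labelled double-blind, and the methods describe masking for the follow-up endoscopists only. This is an omission that the investigators can fill from what they actually do. It is neither a contradiction nor a faulty choice. The design, the 334 patients, the end-point definition and the analysis would be the same with the detail written in.

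The size of any bias cannot be estimated from the document. It is likely small, given the scheduled month-6 endoscopy for all, masked endoscopists, a measured ulcer definition, and a committee that as worded can only confirm or reject what those endoscopists report.

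This conclusion assumes that the trial is run as the Introduction says, with patients and treating clinicians masked and the committee reviewing events without knowledge of allocation. If patients and clinicians turn out not to be masked, the label would be inaccurate and endoscopist-blinded would be the honest description in the report.

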## PATIENTS AND METHODS

### Study population

We will screen for eligible patients who have a past history of gastroduodenal ulcer and underwent endoscopy for dyspeptic symptoms or routine screening, while receiving thienopyridine(either clopidogrel or ticlopidine) therapy to prevent ischemic events. We enroll 334

patients in the study if they meet the following criteria: endoscopic examination reveals normal appearance or pictures of gastritis only; they have received thienopyridine for at least two weeks; they have an atherosclerotic disease such as ischemic heart disease or stroke; they require long-term anti-platelet therapy; and they are adult patients aged  $\geq 20$  years. Patients are excluded if they have a history of gastric or duodenal surgery other than oversewing of a perforation; if they are allergic to the study drugs; if they require long-term treatment with non-steroidal anti- inflammatory drugs (NSAIDs), corticosteroids, aspirin, or anticoagulant agents; if they are pregnant; if they have active cancer, acute serious medical illness or terminal illness; and if they have gastroesophageal reflux disease.

## **Study Protocol**

### ***Randomization and treatment***

Eligible patients are randomly assigned to receive either (1) 40 mg of famotidine daily or (2) 40 mg of pantoprazole daily for 6 months. Randomization is carried out with the use of a computer-generated list of random numbers. An independent staff member assigns the treatments according to consecutive numbers that are kept in sealed envelopes. Anticoagulants, cyclooxygenase-2 inhibitors, conventional NSAIDs, aspirin, over-the-counter analgesics, corticosteroids, misoprostol, sucralfate are prohibited. The administration of an antacid (Iwell, Everest, Taiwan) is permitted for the control of dyspeptic symptoms. Compliance with the regimen is assessed by counting the pills that are returned. If *Helicobacter pylori* (*H pylori*) infection is documented on recruitment, a seven-day course of anti-*H pylori* therapy is administered. Urea breath test is performed at four weeks after the end of anti-*H pylori* therapy.

Blood sampling for genotyping of *CYP2C19* is carried out on enrollment. Platelet aggregation tests are performed in Day 1 and Day 28. The *CYP2C19* genotype is determined using the polymerase chain reaction-restriction fragment length polymorphism (PCR-RFLP) as previous description. Genotypes are classified into three groups: homogeneous extensive metabolizer

(homEM; *CYP2C19\*1/CYP2C19\*1*); heterogeneous extensive metabolizer (hetEM; *CYP2C19\*1/CYP2C19\*2* and *CYP2C19\*1/CYP2C19\*3*); poor metabolizer (PM; *CYP2C19\*2/CYP2C19\*2*, *CYP2C19\*2/CYP2C19\*3*, and *CYP2C19\*3/CYP2C19\*3*).

### ***Follow-up***

Patients are followed up as outpatients with visits every month. Upper gastrointestinal and cardiovascular symptoms are assessed at each visit. They are asked to return to the outpatient clinic if they have persistent dyspeptic symptoms (epigastric pain, fullness, nausea or vomiting) and to report to the emergency room if they have evidences of gastrointestinal bleeding (hematemesis, melena, or sudden onset of severe epigastric pain), cardiovascular events (chest pain, syncope, or sudden onset of severe palpitation) or cerebrovascular accidents (conscious disturbance, hemiparesis, or dysphagia). Follow-up endoscopy with biopsy for urease test is performed whenever persistent dyspepsia, severe epigastric pain, hematemesis or melena occurred and at the end of the 6th month. The endoscopists who performed follow-up endoscopy are unaware of the treatment group assignments. The events of acute coronary syndrome and cerebral vascular accidents during the study period are carefully monitored and assessed.

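### Does naming persistent dyspepsia as an endoscopy trigger in the Follow-up section, but not in the Abstract, bias detection of the primary endpoint?

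*Protocol*

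**What the plan says.** The Abstract of the Protocol (Methods) places follow-up endoscopy at the "end of the 6th month and whenever severe epigastric pain, hematemesis or melena occurs". The Follow-up section says: "Follow-up endoscopy with biopsy for urease test is performed whenever persistent dyspepsia, severe epigastric pain, hematemesis or melena occurred", and also at month 6. The scheduled examination and three of the symptom triggers are common to both; persistent dyspepsia appears only in the second. A nearby sentence in Follow-up, on when patients should return to the clinic, speaks of "persistent dyspeptic symptoms (epigastric pain, fullness, nausea or vomiting") and gives no duration or severity threshold.

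Under End points, "The primary end point is the occurrence of gastric and/or duodenal ulcers, as determined by endoscopy, during the 6-month study period". The same section adds: "Patients who do not have follow-up endoscopic examination are assumed to have had normal findings". It also restricts the analysis to on-treatment events confirmed by an adjudication committee.

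On blinding, the Introduction calls the trial a "randomized double-blind comparison study", and Follow-up states: "The endoscopists who performed follow-up endoscopy are unaware of the treatment group assignments". Randomization and treatment permits antacid for dyspeptic symptoms, without distinguishing the arms.

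**The concern.** The primary endpoint is found only by looking, so the trigger list helps decide how often a patient is looked at. The item missing from the Abstract is the broadest and most subjective one, and both study drugs act on acid-related symptoms. If dyspepsia were commoner on famotidine, that arm would have more unscheduled endoscopies. Two kinds of extra event could follow:

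- ulcers that would have healed before month 6;
- ulcers in patients who skip the month-6 endoscopy and would otherwise be counted as normal.

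Part of an apparent advantage for pantoprazole would then reflect the number of examinations rather than ulcer formation. Staff working from different parts of the Protocol might also apply different rules.

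**Working it through.** The Protocol gives no figure for this point, so there is none to reproduce. The check compares the texts and then sizes the possible bias.

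**Texts side by side**

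| | Abstract | Follow-up |
|---|---|---|
| Month-6 endoscopy for all | yes | yes |
| Severe epigastric pain, hematemesis, melena | yes | yes |
| Persistent dyspepsia | not listed | listed |

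Symptom-driven endoscopy exists under either list. The extra trigger adds to it and does not create it. Its effect is confined to ulcers that the month-6 examination would not show.

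**Inputs**

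- Cumulative ulcer rate p = 11% over 6 months (Introduction, clopidogrel users with an ulcer history), set equal in both arms. That figure is an observed recurrence rate; using it as the rate of all ulcers formed is an assumption.
- Planned N = 334 (Abstract), so 167 per arm if allocation is 1:1 (ratio not stated).
- Assumed: onset uniform over T = 6 months; exponential ulcer lifetime with mean L = 1, 2 or 3 months; one dyspepsia endoscopy, at a random time unrelated to the ulcer, in a fraction f of patients: 30% or 40% in one arm, 10% in the other.

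**Formulas**, each a probability for a patient who forms an ulcer

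- Present at month 6: A = (L/T)(1 − e^(−T/L))
- Present at the random endoscopy: B = (L/T)(1 − A)
- Present at both: C = (L/T)(A − e^(−T/L))
- Detected rate in an arm: p[A + f(B − C)]
- Spurious difference: p × (difference in f) × (B − C)

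**Example, L = 2.** A = 0.3167, B = 0.2278, C = 0.0890, B − C = 0.1388. Month 6 alone detects 0.11 × 0.3167 = 3.5% in either arm.

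- 30% v 10%: 3.94% v 3.64%; difference 0.11 × 0.2 × 0.1388 = 0.31 points.
- 40% v 10%: 4.09% v 3.64%; difference 0.11 × 0.3 × 0.1388 = 0.46 points.

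**All scenarios**

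| L (months) | B − C | 30% v 10% | 40% v 10% |
|---|---|---|---|
| 1 | 0.1117 | 0.25 points (13% relative) | 0.37 points (19%) |
| 2 | 0.1388 | 0.31 points (8%) | 0.46 points (13%) |
| 3 | 0.1353 | 0.30 points (6%) | 0.45 points (9%) |

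The relative excess of 6–19% looks large because the detected base is small. In patients it is 167 × 0.0025 = 0.4 to 167 × 0.0046 = 0.8 per arm.

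**Missed month-6 endoscopy.** If a share q misses it and is counted as normal, the difference is p × (difference in f) × [B − (1 − q)C]. The largest value for q up to 20% (assumed) is at L = 3: 0.11 × 0.3 × (0.2838 − 0.8 × 0.1485) = 0.54 points, or 0.9 of a patient. Over q = 10–20% the relative excess is 7–24%.

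**A broader bound.** Let m be the share of ulcers missed at month 6 and t the share of those caught by a dyspepsia endoscopy. The detected rate is p[(1 − m) + mt], and the difference is p × m × (difference in t). With p = 11%, m = 40% and t = 50% v 20%, it is 0.11 × 0.4 × 0.3 = 1.32 points (167 × 0.0132 = 2.2 patients). The chance of falsely favouring pantoprazole is then about 6.4%, against 2.5% for a two-sided 5% test (assumed). With m = 10% it is at most 3.1%.

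**The obvious remedy.** Suppose ulcers found at dyspepsia-only endoscopy are not counted, and a found ulcer is treated or ends follow-up (the Protocol does not say). The counted rate is then p(A − fC). At L = 2, 40% v 10%: 0.11 × (0.3167 − 0.4 × 0.0890) = 3.09% against 0.11 × (0.3167 − 0.1 × 0.0890) = 3.39%, a spurious −9%. Over all scenarios the range is −3% to −11%.

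**The case for a change.** The best case for acting is that the contradiction is plain and bears on how the primary event is found. An abstract may shorten, but this one sets out a trigger list and omits its most elastic item. Blinded endoscopists and adjudication govern how a lesion is read, not who is referred; if symptoms truly differ by drug, referral can differ under perfect blinding. Dyspepsia is unlikely to be rare, since some patients are recruited after endoscopy for dyspeptic symptoms. Recording the trigger costs little and may be hard to recover later.

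Much of this stands. The lists differ, the mechanism is real, and blinding does not remove it. The direction and the size are not established. No section gives dyspepsia rates by drug, so the three- to four-fold imbalance in endoscopies is an assumption. If dyspepsia is commoner because more ulcers form, finding them is part of the treatment effect and not an artefact. The worry about sites following different texts has little support: the Protocol describes no multiple sites, and staff would be expected to work from the Follow-up section. Counting unscheduled endoscopies per arm by trigger would be enough to show any imbalance, but such tabulation commonly belongs in the SAP, which is not at hand.

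**Conclusion.** No change to the design or the analysis follows. The mismatch is a drafting slip: the Abstract and the Follow-up section should be reconciled so that one list applies throughout, and which list is clinically right is not a statistical question. Aligning the wording would alter neither the trial's conduct, if the detailed section is the one followed, nor its conclusion.

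The ascertainment bias is possible but small: under one patient per arm in the lifetime model, even with a marked imbalance in endoscopies, and about two under the harshest combination tried. These sizes rest on equal ulcer formation at 11%, assumed ulcer lifetimes and endoscopy rates, and 1:1 allocation. An analysis that drops ulcers found at dyspepsia-only endoscopy can err in the opposite direction by a comparable amount, so at most it would serve as a bracket on the primary result.
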